3.1.1 Primary Endpoint(s)

For Aim 1 and Aim 2 we will report descriptive statistics, such as mean, median and standard deviation, for the number of days of use, days of use over 20 hours and average hours of use per day (total hours of use/total days of use) in the study. Secondary Endpoint(s)

For Aim 3. We will conduct explorative data analysis to get preliminary information for designing a full-scale prospective study. First, we will report summary statistics, such as mean, median, standard deviation and quartile range, for continuous measurement and percentage for binary measurement, of heart rate, activity levels, sleep time and quality of sleep for every month and summary statistics for FEV1, BMI and CF exacerbation at enrollment and follow-up visit and differences between enrollment and follow-up visit. To identify what information of heart rate, activity levels, sleep time and quality of sleep is potentially associated with the differences between enrollment and follow-up visit in FEV1 and BMI and CF exacerbation, we will use Pearson correlations for FEV1 and BMI and comparing means or medians of the wearable metrics between the subgroups with and without CF exacerbation in 3 months. We will also consider mean or median values of the wearable metrics measured last 3-/2-/1-month prior to the follow-up to determine the extent to how latest metrics are associated with clinical outcomes.

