Endpoints	Results of the project will allow the CF foundation to determine if integration of these databases is feasible. Ability to develop interventional studies using fitness trackers with interventions with exercise/sleep therapies
Study Design	Single-center pilot, correlational study to provide proof of concept for integrating existing medical data from CFFPR with long term monitoring of patterns in sleep and activity available through individual fitness trackers (i.e. Fitbit).
Study Agent/ Intervention Description	Fitbit tracker; is an activity tracking product that is wireless-enabled wearable technology device that measures data such as the number of steps walked, heart rate, quality of sleep, steps climbed, and other personal metrics involved in fitness
Number of Subjects	21
Duration of Follow up	3-5 Months
Estimated Time to Complete Enrollment:	12 months
Statistical Methodology:	For Aim 1 and Aim 2 we will report descriptive statistics, such as mean, median and standard deviation, for the number of days of use, days of use over 20 hours and average hours of use per day (total hours of use/total days of use) in the study. For Aim 3. We will conduct explorative data analysis to get preliminary information for designing a full-scale prospective study. First, we will report summary statistics, such as mean, median, standard deviation and quartile range, for continuous measurement and percentage for binary measurement, of heart rate, activity levels, sleep time and quality of sleep for every month and summary statistics for FEV1, BMI and CF exacerbation at enrollment and 3-month and differences between enrollment and 3-month. To identify

	what information of heart rate, activity levels, sleep time and quality of sleep is potentially associated with the differences between enrollment and 3-month in FEV1 and BMI and CF exacerbation for 3- month, we will use Pearson correlations for FEV1 and BMI and comparing means or medians of the wearable metrics between the subgroups with and without CF exacerbation in 3 months. We will also consider mean or median values of the wearable metrics measured last 3-2-1-month prior to the follow-up to determine the extent to how latest metrics are associated with clinical outcomes.

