Butler, Konstan, Morgan, & Wohl, 2003) and best practice sharing between centers (Schechter, Fink, Homa, & Goss, 2014). In 2017 all centers have now risen to near real-time reporting of lung function, exacerbation rates, weight and diabetes control trends for patients to encourage conversations and real behavior change around medical adherence.

The objective of this pilot study is to demonstrate the feasibility of integrating the personal health tracker data with the medical data stored in CFFPR to facilitate larger multicenter interventional studies to continue improving care in this deserving population.

Methods

Potential subjects will be identified during regular team meetings held by a dedicated care team for CF patients that includes members of the study staff. Patients who are identified as potential participants will be contacted by a trained member of the study team to discuss participation. The study team will work with patients to arrange for signing of an informed consent form at their next scheduled clinic appointment.

All subjects will be consented to participate in this observational study for a minimum 3 months to accommodate their clinic schedule. There will be a minimum of 2 clinical visits after enrollment (clinical visit 1 at set up and 2-5 months follow up) as well as any sick visits. This visit schedule was selected to coincide with current care schedules.

At the initial visit all consented subjects will be provided a Fitbit Inspire HR and shown the proper use and care of the tracker. The research coordinator will confirm the subject's ability to upload data from the device to their study Fitbit account (deidentified) under direct observation. The subjects will also receive instruction in how to document their activity and sleep in the diary app associated with their Fitbit. (The subjects will have access to instructional videos and help desk

through the Fitbit resource center as well). The research coordinator will monitor the study specific FitaBase for the duration of the study (once a week for 3 months) and contact the patient via their preferred method of contact with encouragement to consistently upload data if needed.

During the initial visit and any follow up clinic visits subjects will complete a general quality of life in CF survey-CF QOL and a sleep quality index-Pittsburgh Sleep Quality Index (PQSI) through Redcap to assist in a comprehensive integration of data.

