2 HYPOTHESIS AND OBJECTIVES

This pilot, single center, correlational study will provide proof of concept for integrating existing medical data from CFFPR with long term monitoring of patterns in sleep and activity available through individual fitness trackers (i.e. Fitbit).

The data collected for each subject from the personal fitness monitors will be trended with daily, weekly and monthly averages over 3 months (activity level, time and intensity of exercise, sleep total time and quality

(percentage deep sleep). This information will be coupled with the CFFPR data health parameters as reported with every clinic visit and any hospitalizations for each subject.

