2.1 Aims

AIM 1: Demonstrate that participants will consistently use and upload data from the fitness tracker as measured by use of at least 20 hours per day and uploading of at least 75% of activity.

AIM 2: Develop integration tool for the data from the Fitbit with data from CFFPR.

AIM 3: Analyze the data trends from the Fitbit for activity and sleep with health trends from the CFFPR (FEV1, BMI, exacerbation rates).

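### Aim 1's whole-study use totals cannot tell early use then abandonment from evenly spread intermittent use, or from full use over a shorter follow-up

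*Combined protocol and SAP*

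**What the plan says.** Section 2.1 sets Aim 1 as: "Demonstrate that participants will consistently use and upload data from the fitness tracker", measured by at least 20 hours of use per day and upload of at least 75% of activity. Section 2 places this within a proof of concept for "long term monitoring of patterns in sleep and activity available through individual fitness trackers".

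For Aim 1, section 3.1.1 plans descriptive statistics on three variables: the number of days of use, and "days of use over 20 hours and average hours of use per day (total hours of use/total days of use) in the study". The Statistical Methodology entry of the protocol summary repeats them, again ending with "average hours of use per day (total hours of use/total days of use) in the study". Each is one value per patient for the whole study.

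Nothing else in the document plans wear time by period:

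- The month-by-month summaries in section 3.1.1 belong to Aim 3 and cover heart rate, activity and sleep.
- The daily, weekly and monthly trending in section 2 lists activity, exercise and sleep, not hours of wear.
- The adherence trend in section 3.1 compares levels of disease severity, not time points.
- The weekly upload checks in section 1 (Methods) are operational.
- Section 9.5 names who provides statistical support and adds no analysis.

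Length of follow-up is stated in different ways: 90 days (section 6.2), a clinic visit 2 to 5 months from enrollment (first exclusion criterion in the protocol summary, and the study calendar) and 3 to 5 months (Duration of Follow up in the protocol summary). Section 9.3 keeps patients who could not complete the downloads in the analysis but does not say how their days without use are counted.

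**The concern.** Consistent use is a statement about how use is spread over time, and none of the planned Aim 1 figures carries that information. Two features make this worse than an ordinary loss of detail. The average is "total hours of use/total days of use", so a patient who stops contributes nothing further to numerator or denominator, and the average stays where it was. The two day counts are bare counts, so their meaning depends on how long the patient was followed, which the document does not fix.

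The pilot is meant to support larger interventional studies. Their designers will need to know whether wear persists or falls away, and the two call for different remedies. Aim 3 also uses wearable metrics from the last 3, 2 and 1 months before follow-up, and a patient who has stopped may have nothing in the shortest window. That is a missing-data matter for Aim 3, but without use by month the reader cannot see how many patients support those analyses.

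**Working it through.** The plan gives no numerical figure for Aim 1. The precision figures in section 9.2 concern Aim 3 and do not bear on this point. The check is whether different patterns of use give different values of the three planned statistics.

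**Inputs**

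- Statistics: section 3.1.1.
- Follow-up F: 90 days (section 6.2). For varying follow-up, 60 and 150 days, which are 2 and 5 months at 30 days per month.
- Assumption: 22 h on every worn day and 0 h on other days. Any constant value above 20 h gives the same ties. At 22 h it makes no difference that Aim 1 says at least 20 h and section 3.1.1 says over 20 h.

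**Formulas**

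- D = days with any use; D20 = days over 20 h; H = total hours = 22 × D.
- Planned average = H / D. For comparison, average over all follow-up days = H / F.
- Monthly share = days with at least 20 h ÷ follow-up days in that month (days 1-30, 31-60, 61-90).

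**Results**

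| Pattern | F | D | D20 | H | H/D | H/F | Share, months 1 / 2 / 3 |
|---|---|---|---|---|---|---|---|
| a. Daily throughout | 90 | 90 | 90 | 1,980 | 22.0 | 22.0 | 100 / 100 / 100% |
| b. Daily to day 60, then none | 90 | 60 | 60 | 1,320 | 22.0 | 14.7 | 100 / 100 / 0% |
| c. 20 of every 30 days | 90 | 60 | 60 | 1,320 | 22.0 | 14.7 | 67 / 67 / 67% |
| d. Daily to day 45, then none | 90 | 45 | 45 | 990 | 22.0 | 11.0 | 100 / 50 / 0% |
| e. Alternate days | 90 | 45 | 45 | 990 | 22.0 | 11.0 | 50 / 50 / 50% |
| f. Daily to a visit at day 60 | 60 | 60 | 60 | 1,320 | 22.0 | 22.0 | 100 / 100 / not followed |
| g. Daily to day 60, none until a visit at day 150 | 150 | 60 | 60 | 1,320 | 22.0 | 8.8 | 100 / 100 / 0% |

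**Reading the table**

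1. The planned average is 22.0 h in every row. It does not register stopping at all.
2. Rows b and c agree on all three planned statistics, and so do d and e. Abandonment and evenly spread intermittent use are indistinguishable when the number of days is the same.
3. Rows f and g agree on all three. Full use over a short follow-up and abandonment within a long one are indistinguishable.
4. Rows a and b differ on both day counts (90 against 60). With equal follow-up, the counts do separate a daily user from a patient who stops.
5. Dividing by all follow-up days separates f from g (22.0 against 8.8 h) but not b from c (14.7 h for both). The monthly share separates b from c, because month 3 is 0 of 30 days against 20 of 30.

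**The case against.** The strongest reply is that the plan hides less than it seems to. A reader might infer that a patient who abandons the device looks just like a steady daily user on every Aim 1 statistic. The document does not support that: over a common 90 days the day counts are 60 against 90. Patient c is also not a consistent user, so the tie is between two kinds of inconsistent use. This stands and limits the point to the situations in items 1 to 3 of the check.

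It can also be said that this is only a denominator problem. That is largely true of the average and of the comparison across follow-up lengths. It is not true of rows b and c, which remain tied over a correct denominator.

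Next, drop-off might show up elsewhere: uploads are confirmed weekly, and the monthly Aim 3 summaries would lose patients. But the weekly check is a management step, and the plan does not say that numbers contributing will be given by month. It might show, but it is not planned to.

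Finally, this is a descriptive pilot of 21 patients with no success threshold for Aim 1, and the detailed data would still exist for a later tabulation. That stands, and it keeps the stakes moderate.

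A reader might also infer that early use is likely to be the best use because support is concentrated at the start. Section 1 (Methods) points the other way: the coordinator monitors once a week for 3 months and will "contact the patient via their preferred method of contact with encouragement to consistently upload data if needed". Nothing in the document says that use declines, and the point does not need it to: the planned figures could not show a decline whether or not one occurs.

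**Conclusion.** The concern holds in limited form. All three Aim 1 statistics are whole-study values, and none can show whether use was sustained. The masking is complete for average hours per day of use, for abandonment against evenly spread use with the same number of days, and for patients followed for different lengths of time. It is not complete for the day counts when follow-up is equal.

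The size is shown by example, not estimated: identical results of 60 days, 60 days and 22 h can go with a third month of 20 qualifying days in 30 or of none. This rests on the illustrative 22 h per worn day and on 30-day months. How many of the 21 patients would follow either pattern cannot be known from the document.

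Two further steps might be inferred and are not supported. Judging consistency on month 3 alone would change Aim 1's question, since a patient with little use in months 1 and 2 and full use in month 3 would pass. Excluding the first 14 days as a familiarisation period has no basis in the document.

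**What to change.** In section 3.1.1 and in the Statistical Methodology entry of the protocol summary, keep the whole-study figures and add, for each study month (days 1-30, 31-60 and 61-90):

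- the share of all follow-up days with at least 20 h of use;
- the mean hours of use over all follow-up days;
- the number of the 21 patients with any use in that month.

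State that days after a patient stops using the device count as non-use while follow-up continues. The denominator needs a defined end of follow-up, so the statements of 90 days, 2 to 5 months and 3 to 5 months have to be reconciled. Show how many patients are under follow-up in each month, so that a visit before day 90 is not read as non-use.

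The cost is a change of wording and a few table rows. Section 1 (Methods) says the study's Fitbit database already reports at daily, weekly and monthly intervals. The downside is that adherence may look less favourable than the whole-study average suggests. The added counts will not fill an empty last-month window in Aim 3, but they will show how many patients had any use in each month.

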Efficacy Assessments	To measure the benefit of using Fitbit trackers for those with CF through evaluating general trends in activity level, intensity of activity and sleep quality and timing (Jankelowitz et al., 2005). Further, integration of data from wearable health tracking with objective biologic/medical data would allow analysis of trends between these core components of a healthy lifestyle and medical outcomes.
Unique Aspects of this Study	This pilot study is to demonstrate the feasibility of integrating the personal health tracker data with the medical data stored in CFFPR to facilitate larger multicenter interventional studies to continue improving care in this deserving population

STUDY CALENDAR

The below study chart is described in detail in Section 5 Study Procedures.

Period/ Procedure	Screening/Enrollment	2-5 monthFollow up visit		Sick Visit
		1	2	
Study Day/Visit Day				
Eligibility Criteria	X			
Informed Consent	X			
Demographics	X			
Assessment of Adverse Events			X	X
Device Administration				
Fitbit Inspire HR provided	X			
Fitbit Training	X			
Sync Device every 5 days	X		X	X
Questionnaires				
CF QOP	X		X	X
PQSI	X		X	X
Medical history collected as standard of care				
Lung Function	X		X	X
BMI	X		X	X

Period/ Procedure	Screening/Enrollment	2-5	Sick Visit
		month	Follow up visit
Study Day/Visit Day	1	2	3
CF exacerbation rate	X	X	X

TABLE OF CONTENTS

PROTOCOL SIGNATURE PAGE	2
REVISION HISTORY	4
PROTOCOL SUMMARY	5
INCLUSION CRITERIA.....	5
EXCLUSION CRITERIA.....	5
FITBIT TRACKER.....	6
STUDY CALENDAR	7
LIST OF ABBREVIATIONS	11
1 BACKGROUND	12
CYSTIC FIBROSIS.....	12
2 HYPOTHESIS AND OBJECTIVES	14
2.1 AIMS	15
AIM 1:	15
AIM 2:	15
AIM 3:	15
3 STUDY DESIGN.....	15
3.1 GENERAL DESCRIPTION	15
3.2 STUDY TIMELINE	16
SEE STUDY CALENDAR.	16
4 PATIENT SELECTION.....	16
4.1 ELIGIBILITY CRITERIA	16
4.2 INCLUSION CRITERIA	16
4.3 EXCLUSION CRITERIA	16
5 STUDY ENTRY AND WITHDRAWAL; STUDY PROCEDURES	16
5.1 STUDY ENTRY PROCEDURES	16
5.2 STUDY WITHDRAWAL PROCEDURES	17
6 TREATMENT PLAN.....	17
6.1 STANDARD OF CARE PROCEDURES	17
6.2 FOLLOW-UP PERIOD	18
7 ADVERSE EVENTS: DEFINITIONS AND REPORTING REQUIREMENTS	19
7.1 DEFINITIONS	19
7.2 MOST MONITORING AND RECORDING AN ADVERSE EVENT	21
8 PHARMACEUTICAL INFORMATION	23
9 STATISTICAL CONSIDERATIONS	23
9.1 STUDY DESIGN	23
9.2 SAMPLE SIZE AND POWER ESTIMATE	23
9.3 REPLACEMENT POLICY	23

9.4 INTERIM ANALYSES AND STOPPING RULES	23
9.5 ANALYSES PLANS	23
9.6 STUDY TEAM	23
9.7 QUALITY ASSURANCE.....	23

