Clinical care visits and hospitalizations during the trial period of three months will be entered into the CFFPR national database (standard practice). Data of specific interest include: lung function (FEV1), BMI, and CF exacerbation rates. The exacerbation will be defined by the treating CF provider (generally this is reported as part of each visit (key features of a CF exacerbation include all the following but does not require any more than 3 of the following: Weight loss (>2 lbs.),

increased cough/increased sputum production, disturbed sleep due to coughing, increased fatigue/inability to do daily activities due to breathing problems/fatigue, fevers, fall in FEV1 by 5% or more)).

Any technical questions from the patient regarding the data collected by the fitness tracker will be answered by the research coordinator.

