3 STUDY DESIGN

3.1 General Description

The study center has identified 147 adult patients ranging from 18 to 69 years of age with CF. For this feasibility study a total of 21 patients will be enrolled and while we will not assign patients to cohorts or limit enrollment based on lung function at the end of the study, we will stratify enrolled patients to explore trends. The cohorts will be constructed ad hoc to facilitate an accurate and clinically meaningful analysis. This will allow for trend analysis to see if more advanced disease is a factor in adherence to use of the Fitbit and an exercise regimen.

The study will be carried out by a dedicated research group consisting of seven full time research coordinators, a research assistant, and a part-time systems specialist within the PI's Division that has conducted numerous trials and continues to support a robust and successful CF research program. The study will be assigned at minimum two research coordinators to provide every eligible patient the opportunity to participate. The study research coordinator group has previous experience with fitness tracker software and management of deidentified database related to a fitness tracker used in a large multicenter clinical trial.

Number of Subjects

Up to 21 patients may be consented into this trial. Twenty-one patients are needed to meet the aims of this trial.

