4.2 Inclusion Criteria

Age >18, Cystic Fibrosis

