9.2 Sample Size and Power Estimate

With sample size 21, we can obtain the following precision: two-sided 95% confidence intervals with a width equal to 0.856 and 0.193 when the estimate of Pearson's correlation between each wearable metric and a clinical outcome is 0.1 and 0.9, respectively (Bonnett, 2000). Regarding mean differences between the subgroup with and without CF exacerbation, we do not know CF exacerbation rate, so consider two scenarios: equal group size (10/group) and 2:1 ratio (7 and 14 group sizes). The two scenarios produce two-sided 95% confidence intervals with a distance from the difference in means to the limits that are equal to 0.940 for the equal size and 0.969(Ostler, 1988) for the latter when the both estimated standard deviations are 1 (we can standardize the wearable metrics and clinical outcomes by dividing raw values by the estimated standard deviation).

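### The Aim 3 correlations with FEV1 and BMI change ignore whether the patient was in an exacerbation at either visit, so they can partly reflect an acute episode

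*Combined protocol and SAP*

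**What the plan says.** Section 3.1.1 (secondary endpoints, Aim 3) takes the difference in FEV1 and in BMI between enrollment and follow-up and relates it to heart rate, activity and sleep: "we will use Pearson correlations for FEV1 and BMI and comparing means or medians of the wearable metrics between the subgroups" with and without exacerbation. It also plans to use wearable values from the last 3, 2 or 1 months before follow-up. The synopsis repeats this method, and Section 9.5 adds none.

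Exacerbation enters Aim 3 in two ways only: as a descriptive summary at the two visits, and as a separate outcome that defines the subgroups. It is not a covariate, restriction or sensitivity analysis for the FEV1 and BMI correlations. The stratification in Section 3.1 is ad hoc, mentions only lung function and disease severity, and is not tied to acute status at a visit.

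The Methods part of Section 1 leaves the diagnosis to the treating provider. The features it lists include weight loss of more than 2 lbs, sleep disturbed by cough, inability to carry out daily activities, and "fevers, fall in FEV1 by 5% or more". Section 4.2 reads in full "Age >18, Cystic Fibrosis", and neither Section 4.3 nor the synopsis asks for clinical stability. The Study Calendar schedules the exacerbation item at enrollment, follow-up and sick visits ("CF exacerbation rate X X X").

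**The concern.** A two-visit change depends heavily on the patient's condition on those two days. If the follow-up visit falls in an exacerbation, FEV1 and weight may be down on that day, and activity and sleep may have been poor over the preceding weeks. Low activity then goes with a fall in FEV1, giving a positive correlation even if activity and lung function have no longer-term link. If the enrollment visit falls in an episode, recovery appears as a gain. That distorts the change score but has less effect on a wearable metric averaged over the following months.

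As written, the analysis cannot tell an acute episode from a longer-term association. Aim 3 exists to give preliminary information for a full-scale study. A larger study using the same method would repeat this bias, because a directional error does not average out with more patients.

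**Working it through.** **1. The plan's own figure.** Section 3.1 gives n = 21 ("Twenty-one patients are needed to meet the aims of this trial"). Section 9.2 states "two-sided 95% confidence intervals with a width equal to 0.856 and 0.193 when the estimate of Pearson's correlation" is 0.1 and 0.9. The Fisher z interval is tanh(atanh(r) ± 1.96/√(n−3)), with 1.96/√18 = 0.462.
- r = 0.1: −0.347 to 0.510, width 0.856.
- r = 0.9: 0.766 to 0.959, width 0.193.

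Both reproduce. The issue is what the correlation measures, not its stated precision.

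**2. How common an episode at a visit would be.** The documents do not say. Section 9.2 states "we do not know CF exacerbation rate, so consider two scenarios: equal group size (10/group) and 2:1 ratio (7 and 14 group sizes"), but those groups describe exacerbation during the study, not on a visit day. I assume 10 to 30% at each visit.

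**3. Episode at follow-up.** Assume no true association and independent status at the two visits. Let p be the per-visit prevalence, d the FEV1 or BMI shift in an episode (in SDs of stable change), and g the shift in the window-averaged wearable metric (in SDs). Episodes at either visit move the change score; only those at follow-up move the metric. Then

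r = p(1−p)dg / √{[1 + 2p(1−p)d²][1 + p(1−p)g²]}.

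For p = 0.2, d = 1, g = 1: 0.16/√(1.32 × 1.16) = 0.13. The last column comes from 20,000 simulated trials of 21 patients.

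| p | d | g | induced r | 95% CI excludes 0 |
|---|---|---|---|---|
| 0.1 | 0.5 | 0.5 | 0.02 | not run |
| 0.1 | 1 | 0.5 | 0.04 | 5.5% |
| 0.2 | 1 | 1 | 0.13 | 8.9% |
| 0.3 | 1 | 1 | 0.16 | 10.4% |
| 0.3 | 2 | 1.5 | 0.32 | 29.7% |
| no effect | 0 | 0 | 0 | 5.1% |

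**4. Why the window matters.** Assume a 1 SD deficit while ill, lasting 2 to 4 weeks, all before the follow-up visit. Averaged over 13 weeks, g is 2/13 to 4/13 = 0.15 to 0.31. Over one month (13/3 = 4.33 weeks), g is 0.46 to 0.92. With p = 0.2 and d = 1 the formula gives r of 0.02 to 0.04 for the 3-month window and 0.06 to 0.12 for the 1-month window.

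**5. Episode at enrollment.** Suppose 4 of 21 patients are affected, so p(1−p) = (4/21)(17/21) = 0.154, with FEV1 change raised by dy and the metric shifted by dx:

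r = p(1−p)·dx·dy / √{[1 + p(1−p)dx²][1 + p(1−p)dy²]}.

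With dx = −1 over the whole window, r is −0.134 (dy = 1) or −0.226 (dy = 2). But the tracker is issued at enrollment, so the window includes recovery. With illness in 2 to 4 of 13 weeks, dx is −0.15 to −0.31 and r is about −0.02 to −0.07. In the last-month window it could be near zero.

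**6. Precision of a sensitivity analysis, at r = 0.1.**
- Partial correlation on status at two visits: SE = 1/√(21−3−2) = 0.25, width 0.901.
- Exclusion of patients affected at either visit: n = 21(1−p)², about 17, 13 or 10 for p of 10, 20 or 30%, with widths 0.95, 1.09 or 1.25.

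**The case against.** The strongest reply is that the plan already separates routine from sick readings. Consent is signed at the next scheduled appointment (Section 1, Methods), follow-up is a routine visit (Section 4.3), and sick visits have their own calendar column with their own lung function and BMI. This stands as mitigation. It does not settle the matter, because nothing says what happens when a patient is found to be exacerbating at a routine visit, or whether a sick visit may serve as follow-up.

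It is also fair that Aim 3 is exploratory, that the planned interval is already 0.856 wide at r = 0.1, and that in three of the four simulated cases the interval excludes zero only 5.5 to 10.4% of the time. Finally, an exacerbation at follow-up is itself an Aim 3 outcome and may lie on the path from low activity to FEV1 loss, so removing it entirely would discard part of what Aim 3 studies. That argues for showing both analyses, not for omitting one.

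Three stronger readings are tempting, and the documents do not support them:
- A reader might infer from the summary of exacerbation at enrollment that the plan expects patients to enter during an episode. The calendar item is an exacerbation rate, so prior history fits the wording equally well.
- A reader might infer that every exacerbation lowers both FEV1 and BMI. The provider makes the diagnosis and no more than three listed features are required, so cough, fatigue and fever could qualify alone.
- A reader might infer that enrollment and follow-up episodes give equal correlations of opposite sign. Steps 4 and 5 show that overlap with the wearable window differs.

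**Conclusion.** The concern holds as a gap in the analysis plan: the FEV1 and BMI correlations do not use exacerbation status, stability is not required at either visit, and the protocol's own definition lets one episode move both sides. With no true association, the induced correlation is about 0.02 to about 0.3, mainly through episodes at follow-up and the last-month window. The enrollment route alone is weaker, about −0.02 to −0.07 under the illness duration assumed.

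Prevalence per visit, shift sizes and illness duration are all assumptions; the documents give none of them. The result does not show that the Aim 3 correlations will be misleading, nor that Section 9.2 is wrong. It shows that the plan could not detect the problem if it arose. For an exploratory secondary aim this is a worthwhile, inexpensive improvement.

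**What to change.** In Section 3.1.1, and correspondingly in the synopsis:

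1. Flag each enrollment and follow-up FEV1 and BMI reading by the exacerbation status recorded at that visit. Report how many patients are affected at each. Since Section 1 says only that status is generally reported, state that it will be recorded at both visits.
2. State whether a sick visit can serve as the follow-up visit.
3. Report the correlations (a) in all patients, as planned, and (b) as a pre-specified sensitivity analysis, either excluding patients in exacerbation at either visit or as a partial correlation adjusting for status at the two visits. Choose the form of (b) in advance.
4. Say in the interpretation whether (a) and (b) agree. Do not carry a correlation seen only in (a) into the full-scale design as a longer-term association.

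Do not substitute readings from outside the wear period, since the change would no longer match the wearable window. Do not make (b) the sole basis for interpretation.

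Eligibility, visits and sample size stay as they are, and the status item is already scheduled. The costs are protocol wording, with approval as an amendment under Section 9.14, and the lower precision of (b) shown in step 6. The adjusted form loses least; exclusion loses more, and with about 10 patients left would be only indicative.

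### The correlations of wearable metrics with FEV1 and BMI change need a baseline-adjusted result beside them as a sensitivity analysis

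*Combined protocol and SAP*

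**What the plan says.** Section 3.1.1 looks for wearable information (heart rate, activity, sleep time, sleep quality) that is "potentially associated with the differences between enrollment and follow-up visit in FEV1 and BMI and CF exacerbation". For the two continuous outcomes the method is bivariate: "we will use Pearson correlations for FEV1 and BMI". The Statistical Methodology entry of the Protocol Summary plans the same for metrics "potentially associated with the differences between enrollment and 3-month in FEV1 and BMI". FEV1 and BMI are also summarised at enrollment, at follow-up and as differences. No partial correlation, regression model or baseline covariate appears anywhere, and section 9.5 says only who will give statistical support.

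Section 3.1 sets no enrollment limit by lung function. It plans to stratify patients at the end of the study, with cohorts formed ad hoc, and gives the purpose as "to see if more advanced disease is a factor in adherence to use of the Fitbit and an exercise regimen".

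Section 9.2 gives precision for unadjusted correlations only: "two-sided 95% confidence intervals with a width equal to 0.856 and 0.193" when the correlation "between each wearable metric and a clinical outcome is 0.1 and 0.9". The Study Calendar lists lung function and BMI at enrollment, so a baseline value is planned for every patient.

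**The concern.** Patients of any severity may enter, and section 3.1 itself allows that more advanced disease may affect device use and exercise. If baseline FEV1 or BMI also predicts how much that measure later changes, a metric can correlate with the change only because both follow baseline. A real association can be hidden in the same way.

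Aim 3 is meant to inform the design of a full-scale study. A metric that mainly reflects where patients started could be carried forward, or a useful one dropped. Unlike sampling error, this bias does not shrink in a larger study. The planned stratification does not answer the question, because it is directed at adherence and is not tied to the FEV1 and BMI correlations.

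**Working it through.** **1. The plan's own figures.** Inputs from section 9.2 are n = 21, two-sided 95% intervals, and r = 0.1 and 0.9. The Fisher interval is tanh(atanh(r) ± 1.96/√(n − 3)).

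- r = 0.1: 0.1003 ± 1.96/√18 = 0.1003 ± 0.4620. The limits are -0.347 and 0.510, so the width is 0.856, as stated.
- r = 0.9: the limits are 0.766 and 0.959, so the width is 0.193, as stated.

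The subgroup half-widths, "equal to 0.940 for the equal size and 0.969", also reproduce from t(0.975, n1 + n2 − 2) × √(1/n1 + 1/n2): 0.9396 for groups of 10 and 10, and 0.9689 for 7 and 14. No stated precision figure is wrong.

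**2. Bias of the raw correlation.** Let a be the correlation of baseline with the wearable metric, and b that of baseline with the change. If metric and change are unrelated given baseline, the expected raw correlation is about a × b. The documents give neither a nor b, so the values below are assumed. The last two columns are simulated (n = 21, 40,000 replicates): the share of correlations that differ from zero in a two-sided 5% t test.

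| a | b | a × b | raw | partial |
|---|---|---|---|---|
| 0.5 | 0 | 0 | 4.9% | 5.0% |
| 0 | -0.5 | 0 | 4.9% | 5.1% |
| 0.3 | -0.2 | -0.06 | 5.7% | 5.0% |
| 0.4 | -0.4 | -0.16 | 10.4% | 5.0% |
| 0.5 | -0.3 | -0.15 | 10.2% | 4.9% |
| 0.5 | -0.5 | -0.25 | 19.5% to 19.9% (two runs) | about 5% |
| 0.7 | -0.5 | -0.35 | 34.8% | 4.9% |

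The first two rows show that both links are needed. With only one of them there is no bias.

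**3. Masking.** With a true partial correlation p, the expected raw correlation is about p√((1 − a²)(1 − b²)) + ab. For p = 0.3:

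- 0.4/-0.4: 0.3 × 0.84 − 0.16 = 0.09
- 0.5/-0.5: 0.3 × 0.75 − 0.25 = -0.025

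**4. The opposite error.** Suppose that the metric tracks true severity (assumed r = 0.5), that true severity does not change, and that each FEV1 reading has reliability R. The raw correlation with change is then exactly 0. Baseline correlates 0.5√R with the metric and −√((1 − R)/2) with the change. The partial correlation is −ab/√((1 − a²)(1 − b²)):

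- R = 0.95: 0.487 × 0.158/0.862 = 0.09
- R = 0.90: 0.474 × 0.224/0.858 = 0.12
- R = 0.80: 0.447 × 0.316/0.849 = 0.17

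**5. Cost of adjusting.** One covariate changes the standard error to 1/√(n − 4) = 1/√17. The width becomes 0.878 at r = 0.1 (limits -0.358 and 0.520) and 0.200 at r = 0.9. These are the raw widths for n = 20, so the cost equals one patient.

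**The case against.** A reader might infer that the plan ignores baseline altogether. It does not: the outcome is a difference, so baseline is subtracted and stable severity cancels, and baseline values are also summarised. What is missing is adjustment, which matters only when both links in step 2 exist.

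A second tempting reading is that the adjusted result is the correct one. The table in step 2 assumes no link given baseline, which is the condition that favours adjustment. With the same baseline correlations but a true raw correlation of zero, the partial correlation averages 0.19 at 0.4/-0.4 and 0.33 at 0.5/-0.5, and is falsely significant in 13% and 31% of studies. Those cases are extreme if baseline error is the only cause: setting √((1 − R)/2) to 0.4 or 0.5 requires R = 0.68 or 0.50. Still, neither analysis is always right, and this part of the objection stands.

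A rule that flags every metric whose sign or size changes on adjustment would also fail. At 0.4/-0.4, raw and partial signs differ in 27% of studies when adjustment is right and in 30% when the raw result is right. The values differ by more than 0.1 in 64% and 72%. Disagreement cannot show which result to trust.

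Finally, Aim 3 is exploratory, speaks of potential association rather than effect, and names no significance test for these correlations. At r = 0.1 the interval runs from about -0.35 to 0.51, so biases of 0.06 to 0.25 lie within sampling error. That limits the importance of the point but does not remove it, since the results are meant to guide a larger study.

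**Conclusion.** The point holds as a modest addition to the analysis. The planned FEV1 and BMI correlations are not adjusted for baseline, and nothing else in the plan would show whether a result depends on it. The possible bias ranges from negligible (-0.06, about 6% nominally significant) through -0.16 (10%) to -0.25 (about 20%). All of this rests on assumed correlations, and the bias is zero if either link is absent. The documents do not support saying that the planned correlations are biased, that a severity difference will pass for an effect of activity or sleep, or that the change score should be replaced. Because each analysis can mislead under different conditions, showing both is better than choosing one. Low priority.

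**What to change.** In section 3.1.1 and the Statistical Methodology entry, keep the raw change-score correlation and add a sensitivity analysis that reports:

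- the partial correlation of each wearable metric with FEV1 (or BMI) change, adjusted for baseline FEV1 (or BMI), with its 95% CI, beside the raw correlation and its CI;
- the correlation of baseline with each metric and with the change, so that the reader can see whether both links are present.

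State that a metric on which the two results disagree will be put forward for the full-scale study with more caution, without presuming that either is correct. State also that all results are associations.

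The cost is a few more lines of analysis on data already planned and one degree of freedom (step 5). Error in a single baseline measurement can distort the adjusted estimate, which is why it should stand beside the raw correlation and not replace it.
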